### 7.2 Patient Discontinuation/Withdrawal from the Study

See the Schedule of Assessments ([Table 1](#), [Table 2](#), [Table 3](#), and [Table 4](#)) for data to be collected at the time of study discontinuation and for any further evaluations that need to be completed.

The Sponsor or its designee must be notified if a patient is withdrawn from study treatment or from the study. The reason(s) for withdrawal must be documented in the patient's medical records and eCRF.

Any patient may be discontinued from the study for any of the following reasons:

- Consent withdrawal at the request of the patient or their legally authorized representative
- AE
- Death
- Investigator decision

- Lost to follow-up
- Significant noncompliance to protocol
- Study termination by Sponsor
- Other

If the patient withdraws consent for disclosure of future information, the sponsor may retain and continue to use any data collected before such a withdrawal of consent.

If a patient withdraws from the study, he/she may request destruction of any samples taken and not tested, and the investigator must document this in the site study records.

### 7.3 Lost to Follow Up

A patient will be considered lost to follow-up if he or she repeatedly fails to return for scheduled visits and is unable to be contacted by the study site.

The following actions must be taken if a patient fails to return to the clinic for a required study visit:

- The site must attempt to contact the patient and reschedule the missed visit as soon as possible and counsel the patient on the importance of maintaining the assigned visit schedule and ascertain whether or not the patient wishes to and/or should continue in the study.
- Before a patient is deemed lost to follow up, the investigator or designee must make every effort to regain contact with the patient (where possible, 3 telephone calls and, if necessary, a certified letter to the patient's last known mailing address or local equivalent methods). These contact attempts should be documented in the patient's medical record.
- Should the patient continue to be unreachable, he/she will be considered to have withdrawn from the study with a primary reason of lost to follow-up.

Discontinuation of specific sites or of the study as a whole are described in Section 10.0.

### 7.4 Replacement of Patients

Patients in Phase 1a dose escalation will be replaced if they are unevaluable for DLT (refer to Section 4.1.1.3).

## 8.0 STUDY ASSESSMENTS AND PROCEDURES

- Study procedures and their timing are summarized in the Schedule of Assessments ([Table 1](#), [Table 2](#), [Table 3](#), and [Table 4](#)). Protocol waivers or exemptions are not allowed.
- Specific clinical laboratory tests to be conducted: [Appendix 1](#)
- Guidance for ECOG assessment: [Appendix 5](#)
- RECIST v1.1: [Appendix 6](#)
- NYHA Classification: [Appendix 7](#)
- Immediate safety concerns should be discussed with the Sponsor immediately upon occurrence or awareness to determine if the patient should continue or discontinue study intervention.
- Adherence to the study design requirements, including those specified in the Schedule of Assessments, is essential and required for study conduct.
- All screening evaluations must be completed and reviewed to confirm that potential patients meet all eligibility criteria. The investigator will maintain a screening log to record details of all patients screened and to confirm eligibility or record reasons for screening failure, as applicable.
- Procedures conducted as part of the patient's routine clinical management (e.g., blood count) and obtained before signing of the ICF may be utilized for screening or baseline purposes provided the procedures met the protocol-specified criteria and were performed within the time frame defined in the Schedule of Assessments.

### 8.1 Efficacy Assessments

#### 8.1.1 Tumor Assessment for the Study

Tumor assessments consist of clinical examination and appropriate imaging techniques (preferably CT scans with appropriate slice thickness per RECIST v 1.1; MRI is acceptable). Assessments should be performed as outlined in the Schedule of Assessments. The same methods used to detect lesions at baseline are to be used to follow the same lesions throughout the clinical study.

Tumor response assessment will be performed by the investigator per RECIST v 1.1 guidelines ([Eisenhauer 2009](#)).

Tumor assessments will be performed at screening, then every 6 weeks from the first dose for 24 weeks, and then every 12 weeks thereafter. Once an initial CR or PR is reported by the investigator, confirmatory scans must be performed 4–6 weeks later.

If patient terminates study treatment prior to scheduled CT/MRI scans, patient should have scans done at the EOT visits (does not need to be repeated if performed within 8 weeks prior to the end of treatment visits, or if tumor progression was previously determined).

After discontinuation of study treatment for reasons other than progressive disease, withdrawal of consent, or initiation of additional anti-cancer therapy, tumor assessments will continue every 12 weeks until disease progression, withdrawal of consent or start of new anti-cancer therapy.

In the Phase 1b portion of the study, patients in LTFU for survival must have tumor scans every 12 weeks if tumor progression was not previously determined and/or use of alternative anti-cancer therapy has not been initiated.

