#### 4.3 Treatment Beyond Disease Progression

For patients in all cohorts, if progressive disease (based on RECIST v1.1) occurs, then the patient may continue to be treated with the scheduled regimen assigned after study enrollment until one of the following criteria is met:

- Confirmed disease progression: The assessment of disease progression by RECIST v1.1 (baseline disease progression assessment) will be confirmed by a repeat evaluation at the next tumor assessment time point, but no sooner than 4 weeks later. If any subsequent tumor assessment time point demonstrates disease progression by RECIST v1.1 or demonstrates further increase in the overall tumor burden (the sum of diameters of target lesions and new lesions), when compared to the baseline disease progression assessment (the sum of diameters of target lesions or the presence of a new lesion), then the subject would be deemed as having confirmed disease progression.
- Meets any of the investigational product discontinuation criteria.
- Clinical symptoms or signs indicating clinically significant disease progression such that the benefit-risk ratio of continuing therapy is no longer justified.
- Rapid disease progression or threat to vital organs/critical anatomical sites (eg, spinal cord compression) requiring urgent alternative medical intervention, and/or continuation of study therapy would prevent institution of such intervention.

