## 7.0 DISCONTINUATION OF STUDY INTERVENTION AND PATIENT DISCONTINUATION/WITHDRAWAL

### 7.1 Discontinuation of Study Intervention

See the Schedule of Assessments ([Table 1](#), [Table 2](#), [Table 3](#), and [Table 4](#)) for data to be collected at the time of treatment discontinuation and for any further evaluations that need to be completed.

Study treatment may be discontinued for any of the following reasons:

- Consent withdrawal at the request of the patient or their legally authorized representative
- Progressive disease as assessed by the investigator. Treatment beyond disease progression may be allowed in select patients in accordance with Section [4.3](#).
- Any event that would pose an unacceptable safety risk to the patient
- A concurrent illness that would affect assessments of the clinical status to a significant degree
- A positive pregnancy test at any time during the study
- Specific request of the Sponsor or its authorized representative (e.g., if the study is terminated for reasons of patient safety)
- AE
- Investigator decision
- Patient decision, non-AE
- Other

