#### 4.4.4. Special notes on response assessment

When nodal disease is included in the sum of target lesions and the nodes decrease to 'normal' size (<10 mm), they may still have a measurement reported on scans. This measurement should be recorded even though the nodes are normal in order not to overstate progression should it be based on increase in size of the nodes. As noted earlier, this means that patients with CR may not have a total sum of 'zero' on the case report form (CRF).

In trials where confirmation of response is required, repeated 'NE' time point assessments may complicate best response determination. The analysis plan for the trial must address how missing data/assessments will be addressed in determination of response and progression. For example, in most trials it is reasonable to consider a patient with time point responses of PR-NE-PR as a confirmed response.

Patients with a global deterioration of health status requiring discontinuation of treatment without objective evidence of disease progression at that time should be reported as 'symptomatic deterioration'. Every effort should be made to document objective progression even after discontinuation of treatment. Symptomatic deterioration is not a descriptor of an objective response: it is a reason for stopping study therapy. The objective response status of such patients is to be determined by evaluation of target and non-target disease as shown in Tables 1–3.

Conditions that define 'early progression, early death and inevaluable' are study specific and should be clearly described in each protocol (depending on treatment duration, treatment periodicity).

In some circumstances it may be difficult to distinguish residual disease from normal tissue. When the evaluation of complete response depends upon this determination, it is recommended that the residual lesion be investigated (fine

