6.2.3 Efficacy Endpoint: DOR

Duration of Response (DOR) is defined as the time from first response (CR or PR determined by the investigator per RECIST v1.1) that is subsequently confirmed until the onset of progressive disease or death from any cause, whichever comes first.

DOR in months will be calculated as: (date of first progression or death from any cause – date of first confirmed CR or PR + 1)/30.4375. Patients who are alive and progression-free at the time of data analysis will be censored at the time of their last assessment for tumor response. DOR for CR and PR patients will be summarized using 25th, 50th (median), and 75th percentiles with associated 2-sided 90% CIs, as well as percentage of censored observations. The median will be estimated by using the Kaplan-Meier method and corresponding 2-sided 90% CI using Brookmeyer and Crowley methodology (using log-log transformation). The detailed censoring rules are displayed in [Table 10](#).

Table 10 Censoring Rules for DOR

Situation	Outcome	Date of Progression or Censoring	Event Description/ Censoring Reason
No baseline tumor assessments	Censored	Date of first dose	No baseline tumor assessment
No baseline tumor assessment, but death within two consecutive tumor assessments period after first dose	Censored	First tumor assessment date	No baseline tumor assessment
No post-baseline tumor assessments and no death	Censored	Date of first dose	No post-baseline tumor assessment

No post-baseline tumor assessment and death after two or more consecutive missing tumor assessments from first dose	Censored	Date of first dose	No post-baseline tumor assessment
Disease progression before receiving subsequent anticancer therapy or data cutoff, whichever happens first	Event	Date of first documented progression per RECIST v1.1 (excludes clinical progression)	PD
Death without documented PD and not receiving new anticancer therapy on or before data cutoff	Event	Date of death	Death
Disease progression or death after two or more consecutive missing tumor assessments	Censored	Date of last evaluable tumor assessment prior to disease progression or death	Two or more consecutive missing tumor assessments
Subsequent anticancer therapy received without documented PD or death prior or on the same day	Censored	Date of last evaluable tumor assessment prior to the date of initiation of subsequent anticancer therapy	Started new anti-myeloma treatment before PD or death.

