CT or MRI	X						X	X	X	Tumor evaluation by CT or MRI should be conducted according to RECIST v1.1 at screening, every 6 (± 1) weeks from the first dose for 24 weeks, and then every 12 (± 2) weeks thereafter. Imaging performed as standard of care may be used if it has been performed within 28 days of treatment. Once an initial CR or PR is noted, confirmatory scans must be performed 4-6 weeks later. Patients who terminate treatment prior to the next scheduled CT or MRI assessment should have a scan performed at the EOT visits (if not conducted in the previous 8 weeks or if tumor progression was previously determined). After discontinuation of study treatment for reasons other than progressive disease, withdrawal of consent, or initiation of additional anti-cancer therapy, tumor assessments will continue approximately every 12 (± 1) weeks until disease progression, withdrawal of consent or start of new anti-cancer therapy. Patients in LTFU for survival must have tumor scans every 12 (±2) weeks if tumor progression was not previously determined and/or use of alternative anti-cancer therapy has not been initiated. Any new anti-cancer therapy should be documented.
Archival Tumor Tissue (or Fresh Biopsy if Archival Not Available)	X									Archival tumor tissue is required. The fresh biopsy required at screening will be accepted in lieu of archival tumor tissue if archival tissue is not available. Blocks are preferred, if not available, a minimum of 15 slides are acceptable.
Sample Collection										
Chemistry	X	X	X	X	X	X	X	X	All samples are assessed locally. Labs may be drawn up to 24 hours in advance of treatment. Additional labs may be performed as clinically indicated.	
Hematology	X	X	X	X	X	X	X	X		
Coagulation	X	X				X	X	X		
Urinalysis	X	X				X	X	X		
HBsAg and HCV RNA	X									
Pregnancy Test	X	X				X			For WOCBP, a serum pregnancy test will be performed at screening (within 7 days of Cycle 1 Day 1) and pregnancy testing will be performed at each subsequent cycle of treatment prior to dosing. All samples are assessed locally.	
PK Sampling		Refer to Protocol Table 4							Blood samples will be collected for PK analyses at the time points specified and submitted to the central laboratory	
PD Sampling		Refer to Protocol Table 4							Blood samples will be collected for PD analyses at the time points specified and submitted to the central laboratory	

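### Phase 1b PFS never counts clinical progression, can censor such patients at their last scan, and has no sensitivity analysis that treats them as failures; ambiguous scan rules can make this worse

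*Protocol*

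**What the plan says.** **Events and censoring.** SAP 6.2.4 defines PFS as time to investigator RECIST v1.1 progression or death from any cause, and takes its censoring rules from Table 10 in SAP 6.2.3. Four rows matter here.

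- The progression event is dated "Date of first documented progression per RECIST v1.1 (excludes clinical progression").
- New anticancer therapy without earlier progression is censored at the last evaluable scan before that therapy.
- "Disease progression or death after two or more consecutive missing tumor assessments" is censored at the last evaluable scan.
- Death without documented progression and without new therapy is an event.

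SAP 6.2 names one sensitivity analysis. It changes the population to the response-evaluable set and leaves the event definition as it is.

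**Stopping treatment.** Protocol 7.1 lists "Progressive disease as assessed by the investigator" as a reason to stop and does not restrict it to RECIST. The response-evaluable definition (Protocol 9.3, SAP 4.5) expressly foresees clinical progressive disease before the first scan.

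**Scans after stopping.** Protocol 8.1.1 has three rules.

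- "After discontinuation of study treatment for reasons other than progressive disease, withdrawal of consent, or initiation of additional anti-cancer therapy, tumor assessments will continue"; the stated interval is 12 weeks.
- A scan is due at the end-of-treatment (EOT) visits unless one was done within 8 weeks or tumor progression was already determined.
- In Phase 1b, "patients in LTFU for survival must have tumor scans every 12 weeks if tumor progression was not previously determined". SAP Appendix 2 repeats this.

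Appendix 6 (RECIST, section 4.4.4), writing of symptomatic deterioration, adds: "Every effort should be made to document objective progression even after discontinuation of treatment".

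**Start of long-term follow-up (LTFU).** The Synopsis, Protocol 4.4 and the survival row of Protocol Table 2 place it after Day 100. The header of Protocol Table 2 and both places in SAP Appendix 2 say Day 28.

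**The concern.** A patient taken off treatment because the disease is clearly advancing has failed, but Table 10 will not record that. Whether the failure is counted later depends on a RECIST scan or a death being captured before new therapy starts and before two assessments go missing. Otherwise the patient is censored at the last scan, or at first dose if alive with no post-baseline scan. This censoring is informative: those removed from the risk set are the ones about to have an event, whereas Kaplan-Meier assumes they fare like those who remain.

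PFS is a secondary endpoint in every Phase 1b cohort, and these are single-arm cohorts, so no comparator carries the same bias and cancels it. The same table governs DOR.

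The scan rules matter because they decide how many clinical progressors later obtain a RECIST event. Neither progressive disease nor tumor progression is tied to RECIST there. A site that records progressive disease as the stop reason could reasonably take all three scan rules as satisfied.

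**Working it through.** **The plan's own figures.** The documents state no PFS assumption, event count or precision. The only numerical basis for cohort size is the exact 90% CI for ORR at n = 25. Its six rows reproduce (for 6/25: 11.0% to 42.0%), but they do not bear on PFS, so size has to be explored under assumptions.

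**Inputs from the documents.** Scans every 6 weeks to week 24, then every 12; every 12 weeks off treatment; Table 10 rules; 30 patients per cohort. The largest median, 4.6 months, is the anti-PD-1 result in renal cell carcinoma quoted as background in Protocol 2.1.

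**Assumed, with ranges.**

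- Exponential failure with median 2, 3 or 4.6 months.
- Clinical-only share of failures f = 10, 20 or 30%.
- Median survival after failure 3 or 6 months.
- 0 or 50% of clinical progressors start new therapy.
- Each later 12-weekly scan has a 70% chance of showing RECIST progression.

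**Hand check.** If every clinical failure were censored when it happened, Kaplan-Meier would estimate S(t)^(1−f) instead of S(t). With median 3 months, S(6) = 0.5^(6/3) = 0.25. With f = 0.20, 0.25^0.8 = 0.330, a rise of 8.0 points. With median 2, 0.125^0.8 = 0.189, a rise of 6.4. With median 4.6, S(6) = 0.405 and 0.405^0.8 = 0.485, a rise of 8.0.

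**Simulation** (100,000 patients per scenario, Kaplan-Meier at 6 months). The reference counts clinical progression on its own date and gives about 14%, 27% and 43% for the three medians. Rises above it, in percentage points:

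| Clinical-only share f | Scans stop; late deaths and new therapy censored | All EOT and LTFU scans done |
|---|---|---|
| 10% | 1.8 to 3.4 | 1.9 to 3.1 |
| 20% | 4.0 to 7.1 | 3.7 to 6.3 |
| 30% | 6.2 to 11.0 | 5.8 to 9.7 |

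In the first column 1.5–2.6, 3.0–5.3 and 4.4–7.9 of 30 patients are censored. In the second, censoring comes only through new therapy: none, or with half starting it 30 × f × 0.5 = 1.5, 3.0 or 4.5 patients.

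The two columns are close. Most of the rise comes from not counting clinical progression and from new-therapy censoring. Stopping scans adds at most about 3 points.

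**Late deaths alone.** Suppose scans stop but late deaths count on the date of death, with clinical progression still not an event. At f = 20% the rise is then 5.7 to 10.0 points (medians 3 and 4.6 months), because the failure is recorded late. Restoring the deaths without the clinical date does not cure the bias.

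**Against cohort precision.** With 27% PFS and n = 30, ignoring censoring, the 90% half-width is about 1.645 × √(0.27 × 0.73 / 30) = 0.133, or 13 points. A shift of 4 to 7 points is roughly a third to a half of that.

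**The case against.** The strongest reply is that the protocol keeps these patients on schedule. The paragraph following the quoted sentence requires 12-weekly scans for Phase 1b patients in LTFU unless tumor progression was determined. Protocol Table 11, under DOR, speaks of tumor progression as objectively documented per RECIST, and Appendix 6 asks sites to keep looking. This stands to the extent that a reader who infers that clinical progressors definitely leave the scan schedule goes further than the text. The wording allows that reading without requiring it. It does not dispose of the point, since the rise is nearly as large with every scan done.

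A reader might also cite Protocol 4.3, where "Clinical symptoms or signs indicating clinically significant disease progression" ends treatment. That criterion applies only to patients already past RECIST progression, who already have a PFS event.

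A reader might construct a patient with stable disease at week 6, stopped at week 9 for clinical progression and dead at week 22, and conclude that PFS is censored at week 6.

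- If the last dose was at week 9, Day 28 is week 13, 7 weeks after the scan, so that scan is waived. Day 100 is week 9 + 14.3 = 23.3, after the death.
- If the last dose was at week 6, Day 100 is week 20.3 and a scan falls due before death.
- In either case censoring at week 6 needs weeks 12 and 18 to count as missing. If scans no longer required are not missing, the death is an event.

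So the example proves no fixed outcome. It shows that Table 10 leaves open what missing means and which row takes precedence.

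Finally, RECIST-only PFS is a legitimate endpoint and follows the stated definition, and all analyses are descriptive, with no hypothesis and no decision rule on PFS. This is correct. It argues for a sensitivity analysis rather than a changed primary definition.

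**Conclusion.** The point holds in this form: Table 10 excludes clinical progression, can censor such patients informatively at their last scan, and is paired with no analysis that counts them as failures. The direction was upward in every scenario examined. The size rests on the clinical-only share, which the documents do not give: about 2 to 3 points on 6-month PFS at 10%, 4 to 7 at 20%, 6 to 11 at 30%, and about 4 to 6 at 20% even with all EOT and LTFU scans done. The remaining assumptions are those listed with the simulation.

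The ambiguous scan rules and the Day 28 versus Day 100 conflict can add to this but are not its main source. Not all deaths are censored; those before two missed assessments, without new therapy, remain events.

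A reader might infer a large shift in median PFS. The documents do not support a headline of that kind: the Kaplan-Meier median sits on scan dates, and when scans stop it moved by 0 to 0.5 month at 10–20% clinical failures and 0 to 2.8 months at 30%, depending on where the median falls.

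No sample size, error rate or dose decision changes. This should be corrected, but it does not undermine the trial.

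**What to change.** 1. **SAP 6.2.4.** Add one prespecified PFS sensitivity analysis in which discontinuation for clinical progression is an event on its date and every death is an event regardless of missed assessments. The two changes belong together, since restoring late deaths alone does not remove the bias.
2. **SAP Table 10.** Define a missing assessment relative to the schedule that applies to the patient at that time (6-weekly, 12-weekly or none), and state which row takes precedence when several apply.
3. **Protocol 8.1.1** (off-treatment, EOT and LTFU sentences) **and the CT/MRI notes of Protocol Tables 1 and 2.** Refer to RECIST v1.1-documented progression, in line with Appendix 6. Carry this into the SAP appendices.
4. **Start of LTFU.** Reconcile the Day 28 and Day 100 passages across both documents.

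Items 1 and 2 need SAP wording and one extra table, using the discontinuation reason and date already collected. Items 3 and 4 are wording changes that keep a few patients on the existing 12-weekly scans. The price is a second, probably slightly less favourable, PFS figure beside the main one.
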